4.3 Efficacy Endpoints

4.3.1 Primary Efficacy Endpoint

Mtb infection is defined in this protocol as QFT conversion from a negative to positive test result, as per the manufacturer's QFT-GIT package insert.

QFT assays will be performed at:

- Screening (used to determine eligibility),
- Day 71 or at the first in-person visit after Day 71 if Day 71 visit was missed or if Day 71 result was not available.
- Every 6 months (counting from Day 1) through Month 48
- Participants who have QFT conversions from a negative to positive test result will have an additional QFT assay three months post initial conversion (Day 84 PC visit).

The primary efficacy outcome measure is sustained QFT conversion in the mITT efficacy population (Section 5.1), defined as primary QFT conversion from QFT-negative to QFT-positive, and sustained

positive QFT tests at both 3- and 6-months after initial (primary) conversion. The initial positive QFT test must be observed after a negative QFT result at Day 71 or at the first in-person visit after Day 71 for which a QFT result is available if the Day 71 visit was missed or if the QFT result at the Day 71 visit was not available.

Due to the required washout period (Section 4.1) and the many Day 71 visits missed due to COVID (lockdown, site closure, etc.), the requirement for a negative QFT test result at Day 71 was extended to include results from the first in-person visit post Day 71. Therefore, throughout this document, Day 71 refers to the Day 71 study visit, or if missing, the first in-person visit post-randomization. Sustained conversion refers to three consecutive positive QFT results following the Day 71 negative QFT result as detailed above. After the initial conversion, a negative or indeterminate result at Post Conversion Day 84 and/or at the biannual visit following the initial conversion would disqualify the conversion event from being a sustained conversion. "Early QFT Reversion" is defined as a reversion from a positive QFT test result to a negative QFT test result at Post Conversion Day 84 or the biannual visit following the initial conversion.

Participants who initially convert to QFT positive at Day 71 will be excluded from the mITT analysis population and the primary endpoint analysis.

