7.2 Determination of Sample Size

The primary analysis will be triggered after the number of required events to achieve 90% power with a 1-sided alpha of 2.5% has been accrued. If the true vaccine efficacy is 45%, at least 118 events are required to achieve 90% power or greater.

The proposed sample size was determined based on targeting a relatively high probability (~80%) of obtaining the required 118 sustained conversion events within 3.5 years of the study start. The probability of obtaining the required 118 sustained conversion events within 3 and 3.5 years of study start are shown in Table 2 for sample sizes ranging from 600 to 800 in the mITT efficacy population, under the assumptions described herein. Due to COVID-19 related restrictions, it will likely take longer to complete enrollment and to reach the number of events needed for the primary analysis.

After accounting for the expected 7% participants to be ineligible for the mITT efficacy population due to a positive QFT assay result at Day 71, the table shows that randomizing approximately 800 participants to each treatment group is sufficient to detect a true VE of at least 45% under the specified assumptions, resulting in ~80% probability to accrue the required number of events (118) within 3.5 years of study initiation when the attack rate is as low as 8%. Since it is expected that approximately 12% of the population enrolled will be 10- or 11-year-old adolescents, where there is limited information on the attack rate and potential VE, a further inflation of the required 800 participants per group by 12% resulted in a final proposed sample size of 900 participants per group, or a total of 1800 participants. Approximately 6720 participants will be screened to enroll and randomize up to 2150 participants.

Table 2: Sample Size Requirements to Ensure 75%-80% Probability of Performing the
Primary Analysis within 3.5 years

	Attack ra	te = 10%	Attack rate = 8%				
N/group	Prob	Prob	Prob	Prob			
mTTT	(analysis	(analysis	(analysis	(analysis			
Efficacy	$in \leq 3$	in ≤3.5	$in \le 3$	in ≤3.5	N/group	N/group	Final N
Population	yrs)	yrs)	yrs)	yrs)	Randomized*	(+12%)**	(Total)
600	4.3	75.4	< 0.1	5.4	646	723	1446
650	21.9	94.0	0.2	20.8	699	783	1566
700	50.4	99.4	0.8	52.7	753	844	1688
750	77.0	>99.9	5.3	80.2	807	904	1808
800	93.0	>99.9	20.5	94.5	861	964	1928

Assumes equal randomization (randomization ratio 1:1)

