Probability analysis occurs within 3 and 3.5 years (yrs) based on 2000 simulations, assuming 1 yr accrual, 70% of primary infection remain sustained, 5% annual drop-out rate

- *Assumes 7% removed from those randomized due to QFT + result at Day 71
- ** Assume additional 12% of participants will be 10 or 11 year olds, where we have limited information on attack rate and potential VE

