9 EFFICACY ANALYSES

9.1 **Primary Analysis**

The primary efficacy endpoint will be analyzed when at least N=118 sustained *Mtb* infection events (defined as QFT conversion from a negative to positive test result, as per QuantiFERON-TB Gold Plus Package Insert) in the mITT population have accrued.

The primary efficacy endpoint (sustained QFT conversion as defined in Section 4.3.1) will be analyzed using a log-rank test, stratified by sex and age group (10-11 years old, 12-14 years old, and >14 years old) to evaluate differences in the distributions of event times between the BCG vaccination and placebo groups.

Censoring and event times will be defined as follows:

- For participants with sustained QFT conversion (censor = 0), time to event will be derived in days as (date of initial conversion date of Day 71 +1) and converted to months. Note that Day 71 here refers to either Day 71 or, if missed, the first in-person visit after Day 71. Date of initial conversion = date of a positive QFT test observed after a negative result at Day 71 or after a negative test at the first in-person visit after Day 71 if the Day 71 visit was missed.
- For participants without sustained QFT conversion (censor = 1), censoring time will be derived in days as (censoring date date of Day 71 + 1) and converted to months. Again, Day 71 refers to either Day 71 or, if missed, the first in-person visit after Day 71.

The censoring date for participants without sustained QFT conversion is the last date at which a non-missing QFT result is available prior to the date of data cut-off. There are several scenarios in which participants may have an initial QFT conversion but fail to meet the requirements for sustained QFT conversion due to subsequent negative, missing, or indeterminate QFT results. Appendix 6 provides details on derivation of event and censoring times for all the expected possible scenarios.

Conventions for additional scenarios not covered in Appendix 6, but based on actual data may need to be considered and detailed in the ADaM specifications prior to all planned analyses. An indeterminate test result will be interpreted as negative for the derivation of a participant's time to event.

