Appendix 5 Prior and Concomitant Medications Date Imputation

Appendix 6 Time to Event Derivation Details

Initial QFT Conversion/ Month 3 post initial conversion/Month 6 post initial conversion ¹	Event/ Censored	Date of Event/Censoring
Sustained conversion prior to date of data cut-off (i.e. Positive/Positive/Positive: -/-/-//+/+/+/any/any)	Event	Date of Initial Conversion to QFT positive
No initial conversion prior to date of data cut-off (-/- /-//-/-)	Censored	Minimum (date of last non-missing QFT result, date of data cut-off)
Initial converters with a 3-month positive QFT and missing 6-month results prior to date of data cut-off (i.e. Positive/ Positive/missing: -/-/-//+/+/- /+/+/Missing)	Censored	Date of initial conversion to QFT positive
Initial converters with a 3-month negative QFT and missing 6-month result prior to date of data cut-off (i.e. Positive/ Negative/Missing: -/-/-//+/-/Missing)	Censored	Date of initial conversion to QFT positive
Initial converters with a missing 3-month and positive 6-month result prior to date of data cut-off (i.e., Positive/Missing/Positive: -/-//+/Missing/+)	Censored	Date of initial conversion to QFT positive
Initial converters with a missing 3-month and negative 6-month results prior to date of data cut-off (i.e. Positive/Missing/Negative: -/-/-//+/Missing/-)	Censored	Date of initial conversion to QFT positive
Initial converters with missing 3-month and missing 6-month results prior to date of data cut-off (i.e., Positive/Missing/Missing: -/-/- //+/Missing/Missing)	Censored	Date of initial conversion to QFT positive

¹indeterminate QFT results are counted a negative test result.

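### SAP Appendix 6 censors two already-disqualified conversion patterns at the date of conversion, against the last-QFT rule in SAP 9.1; the effect is small and the table is easy to align

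*SAP*

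**What the plan says.** Patterns below are written initial / 3-month / 6-month result.

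- **SAP 4.3.1:** "a negative or indeterminate result at Post Conversion Day 84 and/or at the biannual visit following the initial conversion would disqualify the conversion event". One such result is therefore enough to rule out sustained conversion.
- **SAP 9.1, general rule:** "The censoring date for participants without sustained QFT conversion is the last date at which a non-missing QFT result is available" before the data cut-off. The section then points to Appendix 6 for the scenarios it expects, and leaves any others to the ADaM specifications ahead of each planned analysis.
- **SAP Appendix 6:** two rows cover converters with one negative and one missing test: "Initial converters with a 3-month negative QFT and missing 6-month result prior to date of data cut-off" (+/-/missing) and "Initial converters with a missing 3-month and negative 6-month results prior to date of data cut-off" (+/missing/-). Both are censored at the date of initial conversion. The rows +/+/missing, +/missing/+ and +/missing/missing get the same date. A footnote counts indeterminate results as negative.
- **Not listed in Appendix 6:** the fully tested reverters +/-/-, +/+/- and +/-/+.

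**The concern.** Under 4.3.1 the first two patterns are settled: the conversion is not sustained, and the participant was seen event-free at a later date. Appendix 6 stops their clock at conversion, as it does for patterns whose outcome is unknown. The general rule in 9.1 would keep them to the last QFT. The primary time-to-event variable therefore has two conflicting derivations for the same record, and no reason is given.

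The patterns are foreseeable. The plan expects 30% of conversions not to be sustained. COVID-19 restrictions and the bar on blood draws in pregnancy (Protocol 7.4 and 8.2.2) cause missed tests, and an event-driven cut-off can fall before the 6-month test. Nor does management explain the early censoring: under Protocol 8.3.6 transient converters are not referred for preventive therapy, and scheduled testing continues.

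These dates feed the log-rank test, the Cox VE, the incidence-rate denominators and both durability analyses. A second gap concerns row precedence: the SAP does not say which row governs a +/missing/- participant who later shows +/+/+. If the censoring row wins, a real endpoint event is lost.

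**Working it through.** **1. The plan's own figure.** "If the true vaccine efficacy is 45%, at least 118 events are required to achieve 90% power or greater", with one-sided alpha 2.5% and 1:1 allocation (SAP 7.2). By Schoenfeld's formula, events = 4(1.960 + 1.282)² / (ln 0.55)² = 4 × 10.51 / 0.3574 = 117.6, so 118, with power 90.1%. The figure reproduces, and it does not depend on the censoring rule.

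**2. The sections side by side.**

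| Pattern | Status under 4.3.1 | Date under 9.1 | Date in Appendix 6 |
|---|---|---|---|
| +/-/missing | not sustained | last QFT | initial conversion |
| +/missing/- | not sustained | last QFT | initial conversion |
| +/+/missing, +/missing/+, +/missing/missing | unresolved | last QFT | initial conversion |
| +/-/-, +/+/-, +/-/+ | not sustained | last QFT | no row |

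Censoring at conversion is understandable for the third line. The first two lines are the conflict.

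**3. Time lost per participant.** If the rows describe the end of a record, +/-/missing loses 84 days (84/30.44 = 2.8 months) and +/missing/- loses about 6 months. If they also apply when later results exist, the loss can run to the end of follow-up.

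**4. How many participants.** SAP Table 2 assumes "70% of primary infection remain sustained, 5% annual drop-out rate". At 118 events there are 118/0.70 = 168.6 initial conversions, of which 50.6 are not sustained. With each post-conversion test missed independently with probability m, the expected number with exactly one missed is 50.6 × 2m(1-m). Some of these would read +/+/missing and so be unresolved. The documents give no m.

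| m (assumed) | Exactly one test missed | Person-years at 6 months each | Share of about 3,300 |
|---|---|---|---|
| 5% | 4.8 | 2.4 | 0.07% |
| 10% | 9.1 | 4.55 | 0.14% |
| 20% | 16.2 | 8.1 | 0.25% |

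**5. Effect on the Cox VE.** Simulation: 750 per arm, 10% annual attack rate, 1-year accrual, cut-off at 42 months, 5% annual dropout, 120 runs per scenario, unstratified. Half of reverters were assumed negative at 3 months, and reverters kept their ordinary conversion hazard. The rows were applied whatever came later, which is the reading that discards more time. Aligned means known reverters stay at risk to the last QFT. The last two columns apply Appendix 6 with a later sustained conversion ignored or counted.

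| BCG acts on | Missed | Affected, placebo / BCG | Person-years lost | VE aligned | VE App. 6, ignored | VE App. 6, counted |
|---|---|---|---|---|---|---|
| conversion | 5% | 5.3 / 3.1 | 6.0 | 42.8 | 42.8 | 42.9 |
| conversion | 10% | 7.4 / 4.5 | 10.7 | 43.1 | 43.2 | 43.2 |
| conversion | 20% | 12.1 / 6.8 | 20.5 | 43.4 | 43.5 | 43.5 |
| reversion | 5% | 5.3 / 11.0 | 11.1 | 45.9 | 45.9 | 45.8 |
| reversion | 10% | 7.7 / 16.6 | 22.3 | 46.9 | 46.9 | 46.7 |
| reversion | 20% | 11.7 / 23.9 | 38.2 | 46.1 | 45.9 | 45.8 |

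With 10% missed in one arm and 20% in the other, the three VE figures within a scenario again differed by at most 0.3 points. VE itself moved a great deal between those scenarios, but alike under every derivation, so that movement is not due to this rule. Ignoring later events cost 0.1 to 0.5 events per trial. Power moved by 0-2 points, within simulation error.

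**The case against.** **The rows may only describe the end of a record.** The event row of Appendix 6 explicitly allows any results afterwards; the two rows at issue do not. The third row's example shows a reversion followed by a second, incomplete conversion, which suggests that a reverter stays at risk. A reader might infer that two participants, both positive at Month 6 and negative from Month 12 to Month 48, would contribute about 46 and 4 months from Day 71 merely because one missed the 3-month test. That contrast needs the wider reading, which the text does not establish. Even on the narrow reading 3-6 months are lost, and the conflict with 9.1 stands.

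**The handling of fully tested reverters is inferred.** It follows from the default in 9.1, but 9.1 also defers uncovered scenarios to the ADaM specifications, which are not available here. This stands: the gap can be shown, but not how it will be filled.

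**A systematic bias is not shown.** The protocol links reversion to immune control, so a reader might infer that the rule understates VE if BCG promotes reversion. A Month-48 calculation using incidence rates, with 10% missed and reverters staying negative, gives 47.6 BCG and 23.1 placebo person-years lost of about 5,200, and VE of 47.0% against 47.4%. But the primary analysis is at 118 events, SAP 9.1 defines VE from the hazard ratio, and assuming that reverters stay negative makes the discarded time event-free by construction. Step 5 shows 0 to 0.2 points for that mechanism at 10% missed. Sampling error is far larger: the standard error of the log hazard ratio at 118 events is about 2/√118 = 0.18, a 95% interval for VE of roughly 21-62%.

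**Indeterminate results count as negative.** The two rows can therefore include participants whose infection status is not truly known. Their endpoint status is settled by the SAP's own definition, and that is all the point needs.

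**Conclusion.** The conflict is real and concerns the derivation of the primary variable. Two patterns that 4.3.1 already classes as not sustained are censored in Appendix 6 at an earlier date than 9.1 prescribes, and observed event-free time is discarded under either reading of the rows. The size is minor: about 0-0.3 VE points, on the plan's event, sustained-share and dropout assumptions together with an assumed 5-20% of tests missed. The sign depends on whether BCG acts on conversion or reversion and on reverters' later risk. The 118-event design is unaffected. This is a point of specification and consistency; the documents do not support calling it a material bias.

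**What to change.** Before unblinding, edit Appendix 6 as follows.

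1. Censor +/-/missing and +/missing/- at the earlier of the last available QFT and the data cut-off, with the participant still at risk for a later sustained conversion.
2. Add +/-/- and +/+/- with the same rule.
3. Treat +/-/+, and any later re-conversion, as a new conversion sequence, censored at the date of that re-conversion if it is unresolved. Otherwise at-risk time would run through a positive of unknown outcome.
4. State that a later +/+/+ is an event and takes precedence over an earlier censoring row.
5. Leave +/+/missing, +/missing/+ and +/missing/missing unchanged.

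The cost is one SAP table and the matching ADaM derivation, including the precedence logic. No new data are needed and the event target does not change. If an analysis has already been unblinded, keep its derivation and report the aligned version as a disclosed sensitivity analysis.

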Appendix 7 SAS Code

SAS code for all Kaplan-Meier analysis:

```
proc lifetest data = <dataset>;
```

time time*censor(1);

```
strata agegrp sex / group = Treatment test = (logrank);
```

run;

Hazard ratios and 95% confidence intervals will be estimated using a stratified Cox proportional hazard regression model. The following SAS code will be utilized.

```
proc phreg data = <dataset>;
```

```
model time to event (days) * censor (1) = Treatment / risklimits ties=efron;
```

strata agegrp sex;

run;

Proportional hazards assumption will be tested using the following code. Statistical significance of the coefficient associated with the interaction of survival time and treatment group will be assessed at the 0.10 level.

```
proc phreg data = <dataset>;
```

```
model time to event (days) * censor (1) = Treatment trt_time /risklimits ties=efron;
```

strata agegrp sex;

trt_time=treatment*log(time to event);

run;

If the coefficient associated with the function of time is nominally significant at the 0.10 level, then we can use robust sandwich estimate of Lin and Wei (1989) for the covariance matrix.

```
proc phreg data = <dataset> covs;
```

model time to event (days) * censor (1) = Treatment /risklimits ties=efron;

strata agegrp sex;

run;

Interval censoring will be used as sensitivity analysis (based on sustained conversion using 0.35 IU/mL threshold). The following SAS code will be implemented:

proc icphreg data = <dataset>;

```
model (left, right) = Treatment / b=pch(INTERVAL=X);
```

run;

The following SAS code will be implemented to compile CI's based on the mid-p method:

proc freq data=<dataset> order=freq;

tables category / binomial (CL=MIDP);

weight Count;

run;

The following SAS code will be implemented to compile CI's based on the Miettinen and Nurminen method without stratification:

proc freq data=<dataset>;

tables treatment*rate / nocol nopct missing riskdiff (CL=mn);

run;

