10.1 Adverse Events

AEs will be coded using Medical Dictionary for Regulatory Activities (MedDRA) version 22.0 or higher.

AE severity will be graded using the Division of Acquired Immune Deficiency Syndrome (DAIDS) Table for Grading for Intensity (Severity) of Adult and Pediatric Adverse Events Version 2.1, July 2017 as Grade 1 (Mild), Grade 2 (Moderate), Grade 3 (Severe) or Grade 4 (Potentially Life-threatening) on the eCRF.

The following reporting windows are applicable for AEs:

AE Category	Reporting Window
Solicited	Through 7 days post vaccination
Unsolicited	Through 28 days post vaccination
SAEs and AESI	Through 6 months post vaccination
Serious related AEs [ADRs]	Through the end of the study

Only AEs within the reporting window will be included within the relevant category in summary tables. All AEs will be listed, regardless of if it was reported within the applicable reporting window.

Adverse events of special interest (AESIs) are AEs that the sponsor wants to monitor carefully. The following AEs will be collected and reported and summarized as AESIs:

System Organ Class	Preferred Term
Immune system disorders	Anaphylactic reaction
General disorders	Disseminated BCG disease
Infections and Infestations	Osteomyelitis
	Suppurative lymphadenitis
	Injection site abscess
Skin and subcutaneous tissue disorders	Injection site lupus vulgaris

	Injection site keloid formation
Bone disorders	Osteitis

An AE overview table will be generated containing the frequency and percent of participants with at least 1 event as well as total number of reported events in each of the following categories (summarized by treatment group) and also the 95% CI (calculated for a single proportion using mid-p binomial option [refer to Appendix 7]):

- Any AE.
- Unsolicited AEs.
- Related AEs.
- Grade 1 AEs.
- Grade 2 AEs.
- Grade 3 or higher AEs.
- Related, Grade 3 or higher AEs.
- AEs leading to premature study discontinuation.
- AEs of special interest (AESI).
- SAEs.
- SAEs with outcome of death.
- Serious adverse drug reactions (ADRs).

Additionally, the following will be summarized by System Organ Class (SOC) and by preferred term (PT), for each treatment group:

- Incidence of AEs.
- Incidence of AEs by highest grade.
- Incidence of SAEs.
- Incidence of serious ADRs.
- Incidence of unsolicited non-serious AEs.

• AESIs

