10.2.1 Injection Area Symptoms

The proportion of participants reporting each injection area symptom will be presented by treatment group for the safety population. For each injection area symptom, the determination of whether or not the specific symptom occurred on each day and 'Any Day 1 to 7' will be made.

For the 'Any Day 1 to 7' summary tables, the derivation of the proportion is calculated as n1/(n1+n2) where

- n1: Any Day 1 to 7 participant reports the symptom as 'mild', 'moderate' or 'severe' on any Day 1 to 7.
- n2: Participant reports the symptom as 'none' on all 7 days or as a combination of 'none' and missing on all 7 days.

Participants that report the symptom as missing on all 7 days are not included in the proportion calculations.

For redness and swelling, 'mild', 'moderate', and 'severe' categories are based on the largest diameter of the redness or swelling reported in mm and they are age-group specific:

- for participants >15 years: Mild 25 to <50mm; Moderate >=50 to <100 mm; Severe >=100 mm;
- for participants <=15 years: Mild 0 to <=25mm; Moderate >25 to <50 mm; Severe >=50 mm

(refer to the 'Site Reactions to Injections and Infusions' table in Appendix 5 of the study protocol which is based on the Division of AIDS Table for Grading the Intensity [severity] of Adult and Pediatric Adverse Events Version 2.1, July 2017). For participants > 15 years old, 'none' = largest diameter reported on the diary card<25 mm.

95% CI based on the conditional binomial Clopper-Pearson method with mid-p correction (refer to Appendix 7) will be provided.

The maximum severity (highest grading) of each local reaction within 7 days of vaccination will be derived as follows:

- =., if values are missing for all Days 1 to 7.
- =0, if the participant reports all reactions as 'None' or a combination of missing and none for all Day 1 to 7.
- =highest grade (maximum reported severity) within 7 days of vaccination if the answer is not 'None' for at least 1 day.

Results will be summarized for each local reaction reporting n (%) participants by maximum severity within each age group (>15 years and <=15 years).

Duration and Onset Day of Injection Area Symptom:

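### The SAP Appendix 7 mid-p code returns the interval for the commonest level, so any yes/no safety row with incidence below 50% gets the CI for not having the event

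*SAP*

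**What the plan says.** SAP 10.1 plans an overview table: "An AE overview table will be generated containing the frequency and percent of participants with at least 1 event". Its 95% CI is "calculated for a single proportion using mid-p binomial option", with a pointer to Appendix 7.

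SAP 10.2.1 covers the injection area symptoms. For the summary over Days 1 to 7, "the derivation of the proportion is calculated as n1/(n1+n2) where" n1 counts participants who report the symptom and n2 those who do not. The interval is specified as follows: "95% CI based on the conditional binomial Clopper-Pearson method with mid-p correction (refer to Appendix 7) will be provided". SAP 10.2.2 handles general body symptoms in the same way.

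Appendix 7 introduces the code with "The following SAS code will be implemented to compile CI's based on the mid-p method". The procedure line is "proc freq data=<dataset> order=freq" and the request is "tables category / binomial (CL=MIDP", followed by a weight statement on the counts. The block has no LEVEL= option, BY statement, treatment variable or ZEROS option. Nothing elsewhere in the SAP names the event level or tells the programmer to take the complement.

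**The concern.** The text fixes the target as the proportion with the event. The code lets the data choose the target, because the level that is estimated depends on which outcome is more frequent. For rare outcomes that level is absence of the event, so the limits would not belong to the percentage printed beside them.

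Safety and reactogenicity is a secondary objective. Protocol 9.4.2 promises incidences with 95% CIs by treatment group, and the SAP plans no between-arm safety test, so these intervals carry the statement of uncertainty for that objective. For outcomes with few or no events the upper limit is the useful number, and those are the rows where the code returns the wrong level.

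**Working it through.** **Inputs**
- Group size 900, from SAP 7.2.
- Event counts are assumed for illustration, because the documents give no AE rates per arm.
- Two properties of PROC FREQ: ORDER=FREQ lists levels by descending frequency, and BINOMIAL without LEVEL= estimates the first listed level. A third matters for zero cells: observations with zero weight are dropped unless ZEROS is given. These are software behaviour, not statements in the documents, and the code was not run in SAS.

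The plan states no figure that depends on this code, so there is nothing to reproduce first.

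**Formula.** For x events in n, the mid-p 95% limits L and U solve
- P(X > x | L) + ½ P(X = x | L) = 0.025
- P(X < x | U) + ½ P(X = x | U) = 0.025

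with L = 0 when x = 0 and U = 1 when x = n. Replacing x by n − x turns (L, U) into (1 − U, 1 − L).

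**Hand check at x = 0.** ½(1 − U)^900 = 0.025, so U = 1 − 0.05^(1/900) = 0.0033, or 0.33%.

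**Results, n = 900 in one arm**

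| Events (assumed) | CI intended by the SAP text | Level the code selects | CI the code returns |
|---|---|---|---|
| 0 (0%) | 0 to 0.33% | no event | 99.67 to 100% |
| 9 (1%) | 0.49 to 1.83% | no event | 98.17 to 99.51% |
| 36 (4%) | 2.86 to 5.44% | no event | 94.56 to 97.14% |
| 180 (20%) | 17.48 to 22.71% | no event | 77.29 to 82.52% |
| 405 (45%) | 41.77 to 48.26% | no event | 51.74 to 58.23% |
| 441 (49%) | 45.74 to 52.27% | no event | 47.73 to 54.26% |
| 459 (51%) | 47.73 to 54.26% | event | 47.73 to 54.26% |
| 540 (60%) | 56.77 to 63.17% | event | 56.77 to 63.17% |

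The selected level changes at 50%. Above it the code gives what the text asks for; below it the code gives the complement.

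**Two arms in one row.** Assume 60% with BCG and 20% with placebo, and suppose the code is run once per arm. The BCG limits are 56.77 to 63.17% for having the symptom. The placebo limits are 77.29 to 82.52% for not having it, where 17.48 to 22.71% is intended.

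**Multi-level variable.** If the category variable holds several levels, such as severity grades, the code returns one interval, for the commonest grade, and the other rows get none.

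**The case against.** The best defence is that the block is a template. It uses placeholders, other blocks in Appendix 7 would not run as printed either, and it has no treatment variable. A programmer must complete it, and the text of 10.1 and 10.2.1 says plainly which proportion is wanted. Output details are also left to separate documents that may name the level. In part this stands: the intended estimate is not in doubt. But the SAP says the code will be implemented, and the frequency ordering is a positive instruction that leads to the wrong level. It is not an omitted detail.

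The error is also usually easy to see. A row showing 1.0% beside 98.17 to 99.51% contradicts itself, and one minus the printed limits gives the right interval exactly, so no information is lost. That stands, except close to 50%: at 49% the returned interval of 47.73 to 54.26% contains 49% and would look plausible.

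A reader might infer that every safety interval, or most solicited-symptom intervals, would be wrong. The documents do not support this. Mid-p limits are planned only for the overview table and the solicited symptoms; the tables by system organ class and preferred term name no CI. Without per-arm rates one cannot say how many solicited rows fall below 50%. Protocol 8.2.6 describes a local reaction as normal after BCG, so some BCG rows may exceed 50% and come out as intended.

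A reader might also infer that the two arms will be reported for opposite outcomes. That needs by-arm runs, which the by-treatment tables require but the block does not show. It also needs rates on opposite sides of 50%. With a saline placebo this is possible for injection area symptoms, but it is not shown.

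**Conclusion.** The Appendix 7 mid-p code is wrong as written, and the severity is minor. Given the SAS defaults above, every yes/no row of the AE overview and solicited-symptom tables with incidence below 50% in the data analysed would receive the limits for not having the event. The conclusion for such rows is arithmetic; which rows they are depends on rates that the documents do not give, although SAEs, AESIs, deaths and serious ADRs very likely qualify. The mismatch between arms remains a possibility.

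The consequences are contained. No efficacy analysis uses this code and no safety hypothesis is tested. The pausing rules (Protocol 7.1.1, SAP 4.2.3) work on counts and percentages, and the IDMC output list in SAP 4.2.3 names no CIs. It would be wrong to read this as a threat to the safety conclusions.

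**What to change.** In Appendix 7:
- Remove order=freq and process by treatment group.
- Use one yes/no indicator per table row, including one for each severity grade, and name the event level: `binomial(level='Yes' CL=MIDP)`.
- Build the count dataset with an explicit zero-count Yes row and use `weight Count / zeros`. Both parts are needed: ZEROS cannot restore a row that is absent from the input, and naming the level does not help if that level has been dropped.

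With these changes 9 of 900 gives 0.49 to 1.83%, and 0 of 900 gives 0 to 0.33%. The cost is a few words of code and a small step in building the input. No new data and no protocol amendment are needed.
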